11.3.13 Pregnancy Test

Positive pregnancy test results of females of childbearing potential will be presented in a data listing.

11.4 SUBGROUP ANALYSES FOR SAFETY VARIABLES

Subgroup analyses for safety variables are not planned, but may be performed.

12.0 **HEALTH OUTCOMES ANALYSES**

Not applicable.

13.0 **INTERIM ANALYSIS**

No interim analysis is planned for this study. Each database lock will correspond to a milestone and statistical analysis will be provided when all randomized patients have either completed or exited from the targeted visit (Weeks 12, Week 52, and Month 20/Exit).

14.0 **DETERMINATION OF SAMPLE SIZE**

The sample size calculation is based on the primary efficacy analysis of the IOP for US FDA review because the sample size based on the primary efficacy analysis for other regions is expected to be smaller.

The sample size is estimated based on a 2-sided t-test with $\alpha = 0.05$ at each timepoint and the assumption that the mean IOP difference between Bimatoprost SR 10 μg and timolol is -0.25 mm Hg (i.e., Bimatoprost SR 10 μg is 0.25 mm Hg better in IOP-lowering than timolol) at Weeks 2 and 6 and 0 mm Hg at Week 12, with a common SD of 4.0 mm Hg and a common within-subject correlation of 0.6. It is also assumed that the efficacy (IOP-lowering effect) of Bimatoprost SR 15 μg is better than that of Bimatoprost SR 10 μg by 0.25 mm Hg at each timepoint (Hours 0 and 2). These assumptions are based on the data obtained from the ongoing clinical study 192024-041D. Based on simulations, a sample size of 540 patients (180 per group) will provide approximately 95% and 81% power to show noninferiority of Bimatoprost SR 15 μg and Bimatoprost SR 10 μg , respectively, to timolol at all 6 scheduled timepoints based on a noninferiority margin of 1.5 mm Hg and at 3 or more timepoints based on a noninferiority margin of 1.0 mm Hg. Assuming a premature discontinuation rate of 10% within 12 weeks (before primary database lock), approximately 600 patients (200 per group) are to be enrolled into this study.

As part of ongoing centralized data monitoring of masked study data, some of the initial assumptions used for sample size calculation have been revisited. The rate of discontinued or rescued patients in the first 12 weeks is approximately 5%, which was less than the rate of 10% assumed at the study design phase. Furthermore, the masked common IOP variability (pooled standard deviation across treatments and timepoints) is approximately 3.8 mm Hg, which was also less than the assumed 4.0 mm Hg at the study design phase. With the updated assumption on the common IOP standard deviation of 3.8 mm Hg, a sample size of 486 patients (162 per group) would provide approximately 95.1% and 83.5% power to show NI of Bimatoprost SR 15 μg and Bimatoprost SR 10 μg , respectively, to timolol at all 6 scheduled timepoints based on an NI margin of 1.5 mm Hg; and at 3 or more timepoints based on an NI margin of 1.0 mm Hg. With the updated premature discontinuation or rescue rate of 5% within 12 weeks, approximately 510 patients (170 per group) are to be enrolled into this study.

15.0 **STATISTICAL SOFTWARE**

Statistical analyses will be performed using version 9.3 (or newer) of SAS[®].

16.0 DATA HANDLING CONVENTIONS

16.1 VISIT TIME WINDOWS

For all analyses, all follow-up visits or the exit visit will be reassigned with the visit number based on the study days according to the following windows in [Table 16-1](#).

Table 16-1 Visit Time Windows

[figure not shown]
[figure not shown]

Table 16-1 **Visit Time Windows**

If the assessment date (if the assessment date is unavailable, use visit date instead) is on or after the date of the first dose of study treatment, the study day is calculated by assessment date – date of the first dose of study treatment + 1. If the assessment date is before the date of the first dose of study treatment, the study day is calculated by assessment date – date of the first dose of study treatment. Therefore, a negative day indicates a day before the start of the study treatment.

If both scheduled and unscheduled visits occur within a single window, the scheduled visit will be used; and unscheduled visits will be used only if there is no scheduled values available in that window. If multiple visits are eligible for windowing within a single visit window, the visit closest to the target day will be used in the analysis.

If 2 visits are equidistant to the target day, the later visit will be used.

16.2 DERIVED VARIABLES

No Applicable.

16.3 REPEATED OR UNSCHEDULED ASSESSMENTS OF SAFETY PARAMETERS

If a patient has repeated assessments before the start of the first treatment, unless otherwise stated, the results from the final nonmissing assessment made prior to the start of the study treatment will be used as baseline. If end-of-study assessments are repeated or if unscheduled visits occur, the last nonmissing postbaseline assessment will be used as the end-of-study assessment for generating summary statistics. However, all postbaseline assessments will be used for safety evaluation, and all assessments will be presented in the data listings.

16.4 MISSING SEVERITY ASSESSMENT FOR ADVERSE EVENTS

If severity is missing for an AE that started before the date of the first dose of study treatment, an intensity of mild will be assigned. If severity is missing for an AE that started on or after the date of the first dose of study treatment, an intensity of severe will be assigned. The imputed values for severity assessment will be used for the incidence summary; the values will be shown as missing in the data listings.

16.5 MISSING CAUSAL RELATIONSHIP TO STUDY TREATMENT FOR ADVERSE EVENTS

If the causal relationship to the study treatment is missing for an AE that started on or after the date of the first dose of study treatment, a causality of yes will be assigned. The imputed values for causal relationship to study treatment will be used for the incidence summary; the values will be shown as missing in the data listings.

16.6 MISSING DATE INFORMATION FOR ADVERSE EVENTS

The following imputation rules only apply to cases in which the start date for AEs is incomplete (i.e., partly missing).

Missing Month and Day

- If the year of the incomplete start date is the same as the year of the first dose of study treatment, the month and day of the first dose of study treatment will be assigned to the missing fields.
- If the year of the incomplete start date is before the year of the first dose of study treatment, *December 31* will be assigned to the missing fields.
- If the year of the incomplete start date is after the year of the first dose of study treatment, *January 1* will be assigned to the missing fields.

Missing Month Only

- If only the month is missing, the day will be treated as missing and both the month and the day will be replaced according to the above procedure.

Missing Day Only

- If the month and year of the incomplete start date are the same as the month and year of the first dose of study treatment, the day of the first dose of study treatment will be assigned to the missing day.
- If either the year of the incomplete start date is before the year of the date of the first dose of study treatment or if both years are the same but the month of the incomplete start date is before the month of the date of the first dose of study treatment, the last day of the month will be assigned to the missing day.
- If either the year of the incomplete start date is after the year of the date of the first dose of study treatment or if both years are the same but the month of the incomplete start date is after the month of the date of the first dose of study treatment, the first day of the month will be assigned to the missing day.

If the stop date is complete and the imputed start date as above is after the stop date, the start date will be imputed by the stop date.

If the start date is completely missing and the stop date is complete, the following algorithm will be used to impute the start date:

- If the stop date is after the date of the first dose of study treatment, the date of the first dose of study treatment will be assigned to the missing start date.
- If the stop date is before the date of the first dose of study treatment, the stop date will be assigned to the missing start date.

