1.3.3 Clinical Study with Bimatoprost SR

Study 192024-041D was a Phase 1/2, paired-eye comparison evaluating the safety and efficacy of 4 dose strengths of Bimatoprost SR (6 µg, 10 µg, 15 µg, or 20 µg [2 × 10 µg implants]), as single or repeat administration in one eye (study eye), versus the use of topical LUMIGAN[®] 0.03% in the fellow eye (nonstudy eye). The objective of this study was to evaluate the safety and IOP-lowering efficacy of Bimatoprost SR in patients with OAG.

A total of 109 patients received a single administration and 24 patients received a repeat administration of Bimatoprost SR. A trend in dose-response was observed across the 4 dose strengths that were tested. Data suggest that the implant may provide topical prostaglandin analog-like efficacy up to 3 to 4 months post-implantation in the majority of patients. Data following the second administration in the redosed patients showed similar IOP lowering to that observed following the first administration of Bimatoprost SR.

Bimatoprost SR showed an acceptable safety profile with single and repeat administrations in Study 192024-041D. Most adverse events were ocular, mild or moderate in severity, occurred within the first 2 days after Bimatoprost SR administration, and were considered related to the study drug administration procedure. There were no reports of serious study drug-related adverse events, and no new safety concerns were observed after the second treatment. Please refer to the Investigator's Brochure for details on reported safety findings.

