11.1 ADVERSE EVENTS

Adverse events will be coded by SOC and preferred term using the Medical Dictionary for Regulatory Activities.

For a given AE and patient, if more than 1 severity grade is reported, the worst severity grade (the greater of the onset and maximum severity recorded on the electronic case report from [eCRF]), will be used for analysis.

Adverse events will be classified into ocular AEs and nonocular AEs. An ocular AE will be determined as indicated on the AE form of eCRF, and thus are not limited to AEs with primary SOCs of eyes. The treatment-related ocular AEs will be further broken down by either related to injection procedure or related to study drug as indicated on eCRF. Ocular AEs will be tabulated by treatment group for the study eye and pooled for the fellow eye, and nonocular AEs will be summarized by treatment group for patient. Analysis by cycle of treatment will also be performed.

Treatment-Emergent Adverse Events

An AE will be considered a treatment-emergent adverse event (TEAE) for the study treatment period if the AE meets 1 of the following criteria:

- The onset date is on or after the first study treatment date.
- The onset date is before the first study treatment date and either:
 - The severity of the event worsened on or after the first treatment date.
 - The event became serious on or after the first study treatment date.

An AE will be considered as a TEAE for a treatment cycle if the AE meets 1 of the following criteria:

- The onset date is on or after the treatment administration of the cycle but prior to the next cycle administration.
- The onset date is before the treatment administration of the cycle and either:
 - The severity of the event worsened on or after the treatment administration of the cycle.
 - The event became serious on or after the treatment administration of the cycle.

Overall summary of TEAEs will be provided on a per-patient basis for categories of all TEAEs, treatment-related TEAEs, injection procedure-related TEAEs, study drug-related TEAEs, serious TEAEs (STEAEs), deaths, and TEAEs leading to study discontinuation. Each category (except deaths) will be further classified into ocular and nonocular subcategories.

The number and percentage of patients reporting TEAEs will be provided on a per-patient basis by 1) SOC and preferred term; 2) SOC, preferred term and severity in descending order of frequency for each treatment group.

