The number and percentage of patients reporting nonocular TEAEs in each treatment group will be tabulated by SOC and preferred term. Also the number and percentage of patients reporting treatment-related (including study drug related or injection procedure related) nonocular TEAEs in each treatment group will be tabulated by SOC and preferred term.

Similar analyses will be done for ocular TEAEs including 1) by PT and severity; 2) treatment-related TEAEs by PT for each treatment group by study eye and fellow eye. In addition, similar analyses will be performed for ocular TEAEs by treatment cycle.

Within each treatment cycle, ocular TEAEs identified (onset or worsened) within 2 days of administration and identified more than 2 days of administration of each cycle will be summarized by each treatment group for study eye and pooled for fellow eye.

Serious TEAEs

Nonocular and ocular STEAEs will be summarized by preferred term and treatment group, respectively.

TEAEs Leading to Study Discontinuation

Nonocular TEAEs and ocular TEAEs leading to premature discontinuation of the study will be summarized by preferred term and treatment, respectively.

Similarly, ocular TEAEs leading to premature discontinuation will also be tabulated by treatment group by treatment cycle.

Ocular TEAEs Leading to Study Drug Discontinuation or Regimen Change

Ocular TEAEs leading to study drug discontinuation will be summarized by preferred term and treatment for the entire study period and also for each cycle. Ocular TEAEs leading to study drug discontinuation or regimen change are defined as the ocular TEAEs with action regarding study drug reported as “Discontinued” or “Regimen Changed” on the eCRF AE form.

Ocular TEAEs Leading to Implant Removal

Ocular TEAEs leading to implant removal will be summarized by preferred term and treatment for the entire study period and also for each cycle.

TEAEs of Special Interest

Corneal TEAEs and Anterior chamber inflammation TEAEs of interest will be summarized by preferred term and treatment group, respectively. Similar analyses will be done by treatment cycle. The full list of corneal AEs and Anterior chamber inflammation AEs of interest will be provided prior to each database lock.

Additional subcategory of TEAEs may be analyzed separately, such as for ocular TEAE associated with use of a prostaglandin analog (PGA), etc.

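### Partial adverse-event dates are anchored on the first dose only, so missing-day events that follow a repeat injection in the same calendar month are usually credited to the earlier cycle

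*SAP*

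**What the plan says.** SAP 16.6 gives the rules for partly missing adverse-event start dates:

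- **Day missing, month and year of the first dose:** "the day of the first dose of study treatment will be assigned to the missing day".
- **Day missing, any later month:** "the first day of the month will be assigned to the missing day".
- **Month and day missing, year of the first dose:** "the month and day of the first dose of study treatment will be assigned to the missing fields". In a later year the date becomes 1 January.
- **Complete stop date earlier than the imputed start:** "the start date will be imputed by the stop date". This can only move a start date earlier.

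None of these rules refers to the Week 16 or Week 32 administration.

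SAP 11.1 uses those administrations. An event is treatment-emergent for a cycle if "The onset date is on or after the treatment administration of the cycle but prior to the next cycle administration". An event with earlier onset also counts if it became serious in the cycle, or if "The severity of the event worsened on or after the treatment administration of the cycle". The same section plans this split: "Within each treatment cycle, ocular TEAEs identified (onset or worsened) within 2 days of administration", against those identified later. It also plans by-cycle tables for ocular events, for corneal and anterior chamber inflammation events, and for events leading to discontinuation or implant removal.

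**The concern.** The imputation rule and the tables that use it have different reference points. Around injection 1 the rule is conservative: a missing day in the first-dose month puts the event on the injection date. Around injections 2 and 3 it works the other way, because day 1 of the month usually precedes the injection. The event then leaves that injection's 2-day table and appears as a late event of the cycle before.

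Safety after repeated administration is part of the study objective (Protocol 2.1), and early events are the ones most exposed. In the phase 1/2 study most adverse events "occurred within the first 2 days after Bimatoprost SR administration" (Protocol 1.3.3). The SAP is conservative elsewhere: for events starting on or after the first dose, missing severity becomes severe (16.4) and missing causality becomes related (16.5).

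**Working it through.** The documents give no rate of partial dates and no misclassification figure, so there is nothing of the plan's own to reproduce. The check applies SAP 16.6 and then the onset criterion of SAP 11.1.

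**Inputs.** Injections on days 0, 112 and 224 (16-week intervals, Protocol 5.10). Cycles 1 and 2 last 112 days and Cycle 3 lasts 140 days (SAP 11.0). The first dose is taken as equally likely on each of 1,461 consecutive dates, a full four-year calendar with 48 months. Onset timing is assumed. The stop-date rule and the worsening or serious clause are not modelled.

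**Example.** First dose 20 January 2017, second injection 12 May, third 1 September.
- Onset 13 May, day missing: becomes 1 May, credited to Cycle 1 (wrong).
- Onset 21 June, day missing: becomes 1 June, credited to Cycle 2 (right).
- Onset 2 September, day missing: becomes 1 September, credited to Cycle 3 (right, because the injection was on the 1st).

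**Early events, simple count.** Take a 30-day month, injection on any day, onset 0, 1 or 2 days later: 30 × 3 = 90 cases. The cycle is right if the injection is on day 1 (3 cases) or onset falls in the next month (day 29 with offset 2, day 30 with offsets 1 and 2: 3 cases). That is 6/90 = 6.7% right and 93.3% moved back.

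**Early events, real calendar.** At offset k days, the event stays only if the injection was on the 1st or in the last k days of a month. The share moved is 1 − (k + 1) × 48/1,461. Averaged over offsets:

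| Onset after injection | Mean k | Share moved back |
|---|---|---|
| Days 0-1 | 0.5 | 1 − 72/1,461 = 95.1% |
| Days 0-2 | 1 | 1 − 96/1,461 = 93.4% |
| Days 0-6 | 3 | 1 − 192/1,461 = 86.9% |
| Days 0-29 | 14.5 | 1 − 744/1,461 = 49.1% |

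**Onset uniform over the cycle.** In a month of L days, injections on days 2 to L expose L(L − 1)/2 days in total. Over four years: 28 × 465 + 16 × 435 + 3 × 378 + 406 = 21,520. Per injection this is 21,520/1,461 = 14.73 days. The share moved is 14.73/112 = 13.2% for Cycle 2 and 14.73/140 = 10.5% for Cycle 3.

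**Effect on a by-cycle table.** Assume 34 of 170 patients have one event in each cycle, onset is on day 0-1, and a fraction m of events lack the day. Then Cycle 1 shows 34(1 + 0.951m), Cycle 2 loses and gains the same number, and Cycle 3 shows 34(1 − 0.951m).

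| m | Cycle 1 | Cycle 2 | Cycle 3 |
|---|---|---|---|
| 1% | 34.3 | 34.0 | 33.7 |
| 5% | 35.6 | 34.0 | 32.4 |
| 10% | 37.2 | 34.0 | 30.8 |

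At 5%, Cycle 3 loses 34 × 0.05 × 0.951 = 1.6 patients, or about 1 percentage point of 170.

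**The case against.** A reader might infer that missing-day events after injections 2 and 3 generally move back a cycle, and that the plan therefore makes repeat dosing look safer. The documents do not support that, for these reasons:

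- **Only same-month events move.** Onset in a later calendar month than the injection keeps the right cycle.
- **Cycle 2 is not understated on balance.** At equal event rates it gains from Cycle 3 about what it loses to Cycle 1.
- **Early events are the least likely to lack a day.** Adverse events are collected on the administration day and at the Day 2 visit, then by telephone on Days 4 and 8 (Protocol 8 and 8.4.3).
- **Whole-study tables do not change for these events.** Their imputed dates are still on or after the first dose, so they stay in the overall, serious and discontinuation summaries.
- **All three arms share the rule.** It does not favour one arm, although it could narrow a by-cycle difference between arms.
- **Some events return.** The worsening and serious clauses recover part of them, but not a new event that never worsens.
- **Other evidence is untouched.** Visual acuity, hyperaemia, biomicroscopy, implant contact and endothelial cell density (SAP 11.3) do not use adverse-event onset dates.

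All of this stands, and it limits the size of the problem. It does not remove the mismatch: the rule is stated, it would be programmed as written, and it misplaces the events it touches in one direction.

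**Conclusion.** The point holds in a limited form. SAP 16.6 does not suit the by-cycle and 2-day tables of SAP 11.1. Followed as written, it credits about 93-95% of missing-day events starting 0-2 days after a repeat injection to the earlier cycle. With onset uniform over the cycle, the shares are about 13% for Cycle 2 and 10% for Cycle 3. The net tilt is Cycle 1 up and Cycle 3 down.

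The percentages rest on assumed onset timing and evenly spread first-dose dates, and they apply only to events with the day missing. How many there will be is unknown and probably few. A distorted picture of repeat-dose safety is thus a possible small effect, not a demonstrated bias. It justifies a short SAP change and does not call the main safety analysis into question.

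**What to change.** Add to SAP 16.6, for the by-cycle and 2-day tables only: if the day is missing and the known month and year contain a later administration (Week 16 or Week 32, implant or sham), assign the date of that administration. If a complete stop date is before that administration, keep the current 16.6 rule. Whole-study tables stay as they are.

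Without the stop-date fallback, which was not modelled, this reduces backward moves of missing-day events to 0% under every onset assumption above.

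The price is that events which began earlier in that month, before the injection, move forward. By the same 14.73-day count this is about 13% of missing-day events if onset is uniform over Cycle 1 or Cycle 2. They also enter the next injection's 2-day table, as do events that truly began later in the injection month. Both shifts are conservative for repeat dosing and match how injection 1 is already handled. The work is two sentences and a minor programming change, with no effect on efficacy.

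Do not add a similar anchor for dates with only the year known. Assigning the latest administration of that year would replace one arbitrary choice with another; at most it could serve as a sensitivity tabulation.

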16.7 MISSING DATE INFORMATION FOR PRIOR OR CONCOMITANT MEDICATIONS

For prior or concomitant medications, including washout and IOP-lowering medications, incomplete (i.e., partly missing) start dates and/or stop dates will be imputed. When the start date and the stop date are both incomplete for a patient, the start date will be imputed first.

16.7.1 Incomplete Start Date

The following rules will be applied to impute the missing numeric fields for an incomplete prior or concomitant medication start date unless the start date > 1 year is marked. If the stop date is complete (or imputed) and the imputed start date is after the stop date, the start date will be imputed using the stop date. If in the cases that the start date > 1 year is marked, the same month and day of the first dose of study treatment and the previous year of the first dose of study treatment will be assigned to the missing fields.

Missing Month and Day

- If the year of the incomplete start date is the same as the year of the first dose of study treatment, the month and day of the first dose of study treatment will be assigned to the missing fields.
- If the year of the incomplete start date is before the year of the first dose of study treatment, *December 31* will be assigned to the missing fields.
- If the year of the incomplete start date is after the year of the first dose of study treatment, *January 1* will be assigned to the missing fields.

Missing Month Only

- If only the month is missing, the day will be treated as missing and both the month and the day will be replaced according to the above procedure.

Missing Day Only

- If the month and year of the incomplete start date are the same as the month and year of the first dose of study treatment, the day of the first dose of study treatment will be assigned to the missing day.
- If either the year of the incomplete start date is before the year of the date of the first dose of study treatment or if both years are the same but the month of the incomplete start date is before the month of the date of the first dose of study treatment, the last day of the month will be assigned to the missing day.
- If either the year of the incomplete start date is after the year of the date of the first dose of study treatment or if both years are the same but the month of the incomplete start date is after the month of the date of the first dose of study treatment, the first day of the month will be assigned to the missing day.

